5.3 Drug therapy

TPI 287 will be administered on an outpatient basis. Reported adverse events and potential risks are described in Section 7. Appropriate dose modifications are described in Section 6.

TPI 287 Administrations

TPI 287 will be administered as an intravenous infusion over 60 minutes. A window of \pm 15 minutes will be permitted.

Patients will receive the TPI 287 once per week, for total of 3 doses. Treatment with TPI 287 will start the same day of starting FSRT treatment. On the day of FSRT, TPI 287 will be given 4 (+/-2) hours prior to FSRT.

In order to prevent any potential hypersensitivity reactions, all subjects must be premedicated prior to TPI 287 administration. The following drugs and dosing regimens are provided as guidelines for premedication, which must include a corticosteroid, an antihistamine, and an H2 blocker. The concomitant use of steroids in some subjects should be considered in determining the dose of an additional corticosteroid. Oral (PO) dosing as an alternative to IV dosing for premedication is acceptable where appropriate.

Premedication Regimen		
Dexamethasone*	20 mg PO at 12 hours prior and 20 mg PO at 6 hours prior	
Diphenhydramine	50 mg IV push prior	
H2 blocker	IV prior (e.g., Cimetidine 300 mg)	
*In the event that dexamethasone is not available, methylprednisolone may be		
substituted at an equivalent dose (4 mg methylprednisolone = 0.75 mg dexamethasone).		

Subjects will be closely monitored for signs and symptoms of a hypersensitivity reaction during the entire infusion of TPI 287, and 1 hour after completion of TPI 287 infusion. Vital signs will be measured every 30 minutes. If a mild-to-moderate (Grade 1 to 2) hypersensitivity reaction is observed, the TPI 287 infusion will be interrupted. Patient will receive intravenous diphenhydramine 50 mg, hydrocortisone IV 100 mg, and appropriate supportive care until the symptoms resolve. If the signs and symptoms resolve within 1 hour, the TPI 287 infusion will be restarted at a slower infusion rate (half that of the initial attempt), and this slower infusion rate will be used for the remainder of the trial. If the symptoms take longer to resolve, the infusion will not be restarted, and the next dose of TPI 287 will be administered 1 week after the

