5.5 General Concomitant Medication and Supportive Care Guidelines

Because there is a potential for interaction of TPI 287 with other concomitantly administered drugs through the cytochrome P450 system, the use of drugs or herbal supplements that are known to be strong inhibitors/inducers of CYP3A4 and CYP2C8 are not permitted (Appendix B).

Prophylactic use of corticosteroids is allowed during the study to limit symptoms from metastases or radiation.

Non-enzyme inducing anti-epileptic drugs may be utilized to control or prevent seizures.

Principal Investigator should be alerted if the patient is taking any agent known to affect or with the potential to affect selected CYP450 isoenzymes.

5.6 **Duration of Therapy**

Patients will receive TPI 287 on days 1, 8, and 15 (total of 3 doses). On day 1, the TPI 287 will be administered 4 (+/-2) hours prior to FSRT.

5.7 **Duration of Follow Up**

Patients will be seen in follow-up on the 3rd, 6th, 9th, 12th, 15th, and 18th month following the first day of treatment with TPI 287. Patients will be followed for 18 months after first treatment on study or until death, whichever occurs first.

The following will be obtained at pre-treatment evaluation and at each follow up visit: Symptoms history, vital signs/ height and weight, physical examination, KPS/ECOG score, Mini-Mental State Examination, steroid use, quality of life questionnaire, and toxicity evaluation.

Radiologic assessment, MRI brain with and without gadolinium, will be performed at pretreatment and every three months following the end of treatment until the patient is off-study or reaches the 18 month study completion date.

Furthermore, the principal investigator will have close collaboration with oncologists treating the systemic malignancy. Information regarding the status of systemic malignancy such as results of standard imaging evaluations, serum biomarkers measurements, and systemic treatments will be collected and recorded at each visit.

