11.1 Antitumor Effect

Definitions

Evaluable for toxicity. All patients will be evaluable for toxicity from the time of their first treatment with TPI 287.

Evaluable for objective response. Only those patients who have received at least one dose of TPI 287 concurrent with FSRT, and have had their disease re-evaluated will be considered evaluable for response. These patients will have their response classified according to the definitions stated below.

Methods for Evaluation

All measurements should be taken and recorded in metric notation using a ruler or calipers. All baseline evaluations should be performed as closely as possible to the beginning of treatment and never more than 2 weeks before the beginning of the treatment.

The same method of assessment and the same technique should be used to characterize each identified and reported lesion at baseline and during follow-up.

Evaluation of Target Lesions

Complete Response (CR): The tumor is no longer seen on two sequential MRI scans, and the patient is on no steroids or only adrenal-maintenance dose of steroids.

Partial Response (PR): \geq 50% decrease in the product of two diameters of target lesions on two sequential MRIs, taking as reference the baseline product of two diameters, provided that the patient has not had his/her dose of steroids increased since the last evaluation period.

Minor Response (MR): Decrease in diameter products of < 50% on two sequential MRI scans provided that the patient has not had his/her dose of steroids increased since the last evaluation.

Stable Disease (SD): The scan shows no change, taking as reference the smallest product of diameters while on study. Patient should be receiving stable or decreasing doses of steroids.

Progressive Disease (PD): > 25% increase in the product of two diameters of target lesions; taking as reference the smallest product on study (this includes the baseline product if that is the smallest on study), provided that the patient has not had his/her dose of steroids decreased since the last evaluation period. A concomitant decrease in steroid dose will rule out a progression designation at this point. The appearance of one or more new lesions is also considered progressions.

Furthermore, the response will be also measured with RANO working group criteria for metastatic brain tumors when this guideline is published.

Duration of Response

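### The steroid conditions in Section 11.1 let shrinkage on a raised steroid dose count as PR or MR, and leave growth during a steroid decrease with no category, resolution or date

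*Combined protocol and SAP*

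**What the plan says.** Section 11.1 (Evaluation of Target Lesions) gives each category a steroid condition, but not of the same kind.

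- **CR** uses an absolute level: "the patient is on no steroids or only adrenal-maintenance dose of steroids".
- **PR** needs a fall of at least half on two sequential MRIs. One sentence holds two reference points: "reference the baseline product of two diameters, provided that the patient has not had his/her dose of steroids increased since the last evaluation period".
- **MR** reads "Decrease in diameter products of < 50% on two sequential MRI scans provided that the patient has not had his/her dose of steroids increased", again looking back only to the last evaluation. It names no size reference.
- **SD** needs an unchanged scan on a stable or falling steroid dose.
- **PD** is growth above 25% over the smallest product on study, baseline included, with no steroid decrease since the last evaluation. The section adds: "A concomitant decrease in steroid dose will rule out a progression designation at this point". The sentence after that counts new lesions as progression and sets no steroid condition.

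Steroid changes are foreseeable. Section 5.5 says: "Prophylactic use of corticosteroids is allowed during the study to limit symptoms from metastases or radiation". Section 5.3 requires a corticosteroid before every TPI 287 infusion; its guideline dexamethasone regimen is "20 mg PO at 12 hours prior and 20 mg PO at 6 hours prior". Infusions fall on days 1, 8 and 15 (Section 5.6). MRI is done at baseline and then every 3 months (Sections 5.7 and 10). Section 11 orders a confirmatory MRI 4 weeks after a first response, but nothing comparable for growth that may not be called PD.

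**The concern.** There are two separate gaps and one ambiguity.

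1. PR compares size with baseline but steroid dose with a more recent point. An increase that persists is seen once and then drops out of the look-back, so shrinkage that may be due to the higher dose can be credited as response. MR has the same look-back.
2. Any steroid decrease, however small, bars size-based PD, however large the growth. The scan then has no category, because SD requires an unchanged scan, and nothing says when or how the growth is settled or which date it takes.
3. The last evaluation is not defined, and nothing says whether premedication pulses count as changes in steroid dose.

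Anti-tumour effect is a secondary objective, and the 10-patient expansion is partly there to assess radiologic response. PFS and the durations of response and stable disease depend on when progression is declared.

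**Working it through.** The plan states no response rate, power or timing figure on this point, so there is none to reproduce. The check applies the written rules to simple steroid courses. The courses are illustrative assumptions; the documents give no rate of steroid changes.

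**Timeline (3 months = 91 days)**
- Last infusion: day 15.
- Final visit: 15 + 30 = day 45. Steroid use is assessed, but the study calendar marks no MRI.
- First on-study MRI: 15 + 91 = day 106, counting from the end of treatment. Other anchors in Sections 5.7 and 10 give 1 + 91 = day 92 or 45 + 84 = day 129.
- Later MRIs: 106 + 91 = day 197, then days 288 and 379.

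**Three readings of the steroid look-back**
- A: back to the previous response MRI (or baseline), any change counting.
- B: back to the previous visit with a steroid assessment, which for the first MRI is the final visit.
- C: net change in dose between response MRIs.

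**Three courses**
- Rise: dose doubled on day 20 and then constant, with a lasting fall of at least 50% in tumour product.
- Taper: one decrease on day 60, with growth above 25% at the first MRI.
- Premedication only: constant background dose.

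| Reading | Rise: PR barred at day 106 / 197 | Taper: size-based PD barred at day 106 / 197 | Premedication only, day 106: PR barred / PD barred |
|---|---|---|---|
| A | yes / no | yes / no | yes / yes |
| B | no / no | yes / no | no / no |
| C | yes / no | yes / no | no / no |

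**PR and MR.** Under every reading the day-20 rise no longer bars response at day 197, although the dose is still twice baseline. Under B it never bars it. PR can then be met on two sequential MRIs.

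**PD.** Under every reading the growth at day 106 is not PD. It can first be called at day 197, a delay of 197 − 106 = 91 days. If the dose steps down in each of three successive intervals (days 60, 150 and 240), the scans at days 106, 197 and 288 are all barred. The first scan free of the bar is day 379, a delay of 379 − 106 = 273 days. At the month-18 scan there is no later scheduled scan, so barred growth may never be recorded as PD.

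**Premedication.** The guideline regimen is 2 × 20 = 40 mg dexamethasone per infusion, or 3 × 40 = 120 mg in all, and it ends by day 15. That is 77, 91 or 114 days before the first MRI, depending on the anchor (92 − 15, 106 − 15, 129 − 15). Only reading A makes it count.

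**Scale.** With 10 patients, one reclassified patient moves the response rate by 10 points. For example, 6/10 has an exact 95% interval of 26% to 88%, and 7/10 has 35% to 93%.

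**The case against.** The bar on PD has a proper purpose: it stops an effect of steroid withdrawal from being called progression. It applies only for the time being, so the usual result is delay. New lesions count regardless, and death is a PFS event in any case. Section 11 has scan readings corrected against the clinical course, and Section 11.1 promises RANO criteria once published. Response is not primary, the analysis is descriptive, and neither the escalation rules (Section 5.4) nor the stopping rules (Section 5.9) use these categories.

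All of that stands, and it limits the consequence. None of it supplies the missing rule: the clinical correction sets no steroid criterion, and RANO is an addition that depended on later publication. The purpose of the bar justifies deferring the call, but not leaving the scan unclassified and undated.

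A reader might infer more than the documents support:

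- **That premedication blocks both PR and PD for every patient at the first scan.** This needs reading A with transient changes counted. Section 5.3 itself separates a patient's concomitant steroids from the additional premedication dose. Only a corticosteroid is mandatory; the dexamethasone schedule is a guideline. What remains is an ambiguity.
- **That every error favours TPI 287.** The PR and PD gaps do, but the premedication reading would also bar PR and MR, which works against showing response.
- **That local control is affected.** It is listed as an endpoint in Section 14.1 but never defined or tied to these categories. The link to PFS is an inference too, though a natural one, since Section 11.2 uses progression without another definition.
- **That CR shares the flaw.** Its condition is an absolute steroid level, so it does not.

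**Conclusion.** The point holds in limited form. Followed exactly, Section 11.1 can class shrinkage on a dose above baseline as PR or MR from the second evaluation on. It can also record true target-lesion progression one 3-month scan late or more, or not at all if the growth is first seen at the last scan. Both results hold under all three readings of the look-back. The 91- and 273-day delays rest on the assumed steroid courses and apply only where the barred growth is true progression, no new lesion appears and the patient survives to the next scan. How many patients this would touch cannot be estimated from the documents, but in a cohort of 10 each one is worth 10 points. The premedication issue is a wording ambiguity to be closed. MTD and DLT decisions are untouched. This should be corrected because the remedy is cheap and the response and PFS summaries depend on it.

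**What to change.** Change the wording of Section 11.1 only:

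- **PR and MR.** Keep the no-increase condition and add that the steroid dose at both sequential scans is no higher than at the baseline scan. Leave CR as it is.
- **PD.** Replace the bar with deferral. Growth above 25% during a steroid decrease is classed as indeterminate. Confirm PD if the next scan, with no further steroid decrease, still shows more than 25% over the same nadir, or if a new lesion has appeared. Date size-based PD to the first scan. State that new lesions are never deferred.
- **Unresolved growth.** Report indeterminate growth that is never settled, and add a sensitivity analysis that counts it as PD.
- **Definitions.** Define the last evaluation as the previous response MRI, and exclude TPI 287 premedication from steroid dose for response classification.

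No visit or scan is added. Steroid use is already assessed at every visit in the study calendar, and the current criteria already need the dose at each scan. The price is that some PRs and MRs are lost and PFS is slightly shorter. No dose or clinical rule changes.

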3. PATIENT SELECTION

3.1 Eligibility Criteria

- Patients must have histologically or cytologically confirmed non-central nervous system primary breast or non-small cell lung cancer.
- Patients must have pathologically or radiologically confirmed metastatic disease in the brain.
- Patients with up to 3 brain metastases (symptomatic and non-symptomatic) can be treated on this study. Maximum diameter of each brain lesion should be ≤ 5 cm. Maximum tumor volume ≤ 120 cc
- Age ≥ 18 years.
- ECOG performance status ≤ 2 (Karnofsky $\geq 60\%$, see Appendix A).
- Life expectancy of greater than 12 weeks.
- Patients requiring treatment with corticosteroids are eligible.
- Treatment with non-enzyme inducing anti-seizure medications is allowed.
- Patients must have normal organ and marrow function as defined below:
 - leukocytes ≥3,000/mcL
 - absolute neutrophil count \geq 1,500/mcL
 - platelets $\geq 100,000/mcL$
 - total bilirubin within normal institutional limits
 - AS T(SGOT)/ALT (SGPT) ≤2.5 × institutional upper limit of normal
 - creatinine within normal institutional limits OR
 - calculated creatinine clearance $\geq 60 \text{ mL/min}/1.73 \text{ m}^2$ for patients with creatinine levels above institutional normal.
- Systemic chemotherapy washout period ≥ 7 days. For investigational dugs and monoclonal antibodies washout period $\geq 5x$ drug half-life. There are no limitations on

number of prior treatment regimens.

- The effects of TPI 287on the developing human fetus is unknown. For this reason, women of child-bearing potential and men must agree to use adequate contraception (hormonal or barrier method of birth control; abstinence) prior to study entry and for the duration of study participation. Should a woman become pregnant or suspect she is pregnant while she or her partner is participating in this study, she should inform her treating physician immediately. Men treated or enrolled on this protocol must also agree to use adequate contraception prior to the study, for the duration of study participation, and 4 months after completion of TPI 287 administration.
- Prior brain surgery or radiation is allowed as long as the metastatic lesion(s) to be targeted in this study has not previously been treated with radiation.
- Ability to understand and the willingness to sign a written informed consent document.

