3.2 Exclusion Criteria

- Patients who have had chemotherapy within 1 week (6 weeks for nitrosoureas or mitomycin C) or investigational therapies/monoclonal antibodies within 5 half-life of investigational compound or those who have not recovered from adverse events due to agents administered more than 1 week earlier. Bisphosphonates, endocrine therapy, and trastuzumab are permitted without restriction.
- Patients who are receiving any other investigational agents.
- Previous treatment of the target lesions with radiation therapy.
- Patients who have previously been treated with whole brain radiation.
- History of allergic reactions attributed to compounds of similar chemical or biologic composition to TPI 287.
- Pregnant women are excluded from this study because TPI 287 is an agent with an unknown but potential risk for teratogenic or abortifacient effects. Because there is an unknown but potential risk for adverse events in nursing infants secondary to treatment of the mother with TPI 287, breastfeeding should be discontinued if the mother is treated with TPI 287.
- Known contraindication to enhanced MRI and CT scan.

 Uncontrolled intercurrent illness including, but not limited to, ongoing or active infection, symptomatic congestive heart failure, unstable angina pectoris, cardiac arrhythmia, uncontrolled seizure activity or psychiatric illness/social situations that would limit compliance with study requirements.

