5.9 Stopping Rules

The expected rate of neurologic death with FSRT alone is 13-14%. ^{24,25} The reported rate for symptomatic radiation necrosis is 7.7%. ²⁴ A higher rate of neurologic death (> 14%) or symptomatic brain necrosis (> 10%) in this study would imply that the combination of FSRT and TPI 287 is excessively toxic and not suitable for further clinical development. In addition grade \geq 3 delayed-onset toxicity in this study would imply that the combination of FSRT and TPI 287 is excessively toxic and not suitable for further clinical development. In addition, the results will be discussed with Cortice Bioscience, Protocol Monitoring Committee and IRB and study will be closed. In addition, occurrence of other delayed-onset treatment related grade 3 or higher CNS- toxicity will be monitored closely and reviewed with Protocol Monitoring Committee and IRB to determine whether discontinuation of trial is subsequently warranted.

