11.2 Criteria for Evaluation of Therapy Effectiveness

Progression-Free Survival

PFS is defined as the duration of time from start of treatment to time of progression or death, whichever occurs first.

Quality of life

Quality of life will be measured using the EORTC QLQ-BN20+2 and QLQ-C15-PAL questionnaires. These questionnaires will be given to the patient at the same time points as MMSE during the follow up visits.

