14. STATISTICAL CONSIDERATIONS

14.1 Study Design/Endpoints

This is a standard 3+3 design and will include 2 cohorts: 1) dose escalation cohort, and 2) dose expansion cohort.

Endpoints

• Primary endpoints

- To determine the maximum tolerated dose (MTD) of TPI 287 given concurrently with FSRT to treat brain metastases from advanced breast and non-small cell lung cancer
- To determine the safety and toxicity of TPI 287 given concurrently with FSRT to treat brain metastases from advanced breast and non-small cell lung cancer

• Secondary endpoints

- To determine the local control rate
- To determine the distant intra-cranial control rate
- To determine the short-term (≤ 30 days post-treatment) and long-term (> 30 days post treatment) adverse effects
- To determine the PFS
- To evaluate the effect of concurrent therapy with TPI 287 and FSRT on measures of quality of life

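### Under section 11.1, growth of a known brain lesion that is not a study target is not progression, so PFS misses that failure

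*Combined protocol and SAP*

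**What the plan says.** **Entry.** Section 3.1 states: "Prior brain surgery or radiation is allowed as long as the metastatic lesion(s) to be targeted in this study has not previously been treated"; the treatment meant there is radiation. Section 3.2 excludes "Previous treatment of the target lesions with radiation therapy" and, separately, earlier whole brain radiation. The synopsis describes the eligible metastases as ones without previous brain radiation, which can be read more strictly.

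**Progression.** In section 11.1, PD is a more than 25% "increase in the product of two diameters of target lesions; taking as reference the smallest product on study". The one further route is: "The appearance of one or more new lesions is also considered progressions". There is no category for existing lesions that are not targets.

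**Endpoints.** Section 11.2 says: "PFS is defined as the duration of time from start of treatment to time of progression or death, whichever occurs first". Section 14.1 lists "To determine the distant intra-cranial control rate" among the secondary endpoints; neither that section nor the synopsis says what a distant failure is.

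**Necrosis.** Section 5.9 says that a rate of "symptomatic brain necrosis (> 10%) in this study would imply that the combination of FSRT and TPI 287 is excessively toxic", and that the results go to the "Protocol Monitoring Committee and IRB and study will be closed". Section 5.4, by contrast, requires a DLT to be at least possibly related to study treatment and confines delayed CNS DLTs to the irradiated volume. The text after Table 2 refers to the radiation field.

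**The concern.** A patient may enter with one metastasis irradiated focally before the trial and another never irradiated. Only the second can be a target. If the first regrows, the patient has failed in the brain, but section 11.1 has no rule that records it.

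This matters because less distant brain failure is half of the hypothesis in the synopsis, and PFS is a listed endpoint. It can also put sections of the plan at odds. Section 5.8 removes a patient whose progression needs whole brain radiation, and still follows removed patients for progression. A patient could be removed because an old lesion grew and then be followed under a definition that cannot register that growth.

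A related question arises for safety. Section 5.9 does not say whether necrosis at a site irradiated before the trial enters the rate that leads to closure.

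**Working it through.** **1. Can such a patient enter?** Take two metastases, A irradiated focally before the trial and B never irradiated. Two is within the limit of three in section 3.1. B may be targeted. A may not, because section 3.2 bars targets with earlier radiation. The patient is eligible on the detailed criteria, and A is a known, non-target lesion.

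**2. Apply the PD definition to growth of A.**

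| Route in 11.1 | Met by growth of A? |
|---|---|
| More than 25% growth of target lesions | No, A is not a target |
| New lesion | No, A is on the baseline MRI |

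The result is no PD.

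**3. Carry this into PFS.** Section 11.2 uses progression or death and gives no other definition of progression. The recorded event waits for target growth, a new lesion or death, so recorded PFS is never shorter than PFS with growth of A counted. MRI is three-monthly and follow-up ends at 18 months. If A grows by about month 3 and nothing else happens, that patient's PFS is too long by up to about 18 − 3 = 15 months. If another event comes first, nothing is lost.

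**4. Distant control.** The endpoint is named without a definition, so the text classes growth of A neither as failure nor as success.

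**5. Size.** The plan's escalation maximum reproduces: 6 upward dose levels × 6 patients = 36. The cohort at the MTD is 10, including its escalation patients. One unrecorded failure shifts a proportion by:

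- 1/10 = 10 percentage points in the MTD cohort;
- 1/36 = 2.8 points in a full escalation phase.

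The documents do not give the share of patients with such a lesion, so no total can be derived.

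**6. Why the scope of the necrosis count matters.** The limit is more than 10%.

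| Patients | Largest count not above 10% | Smallest count above 10% |
|---|---|---|
| 9 | 0 | 1 (11.1%) |
| 10 | 1 (10.0%) | 2 (20.0%) |
| 36 | 3 (8.3%) | 4 (11.1%) |
| 40 | 4 (10.0%) | 5 (12.5%) |

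Forty is 36 + 4, if the MTD level already holds six. Section 5.9 does not state the denominator. Using its 7.7% reference rate, with patients independent:

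- the chance of exceeding 10% among 10 patients is 1 − 0.923^10 − 10 × 0.077 × 0.923^9 = 17.7%;
- if one of the ten already counts through an old site, one more among the other nine suffices: 1 − 0.923^9 = 51.4%.

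At these sizes, whether a single old-site event counts can decide the outcome.

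**The case against.** **The synopsis may remove the case.** Read strictly, it bars any earlier brain radiation. Sections 3.1 and 3.2 are more specific and allow it, so the gap stands, but the conflict itself needs resolving.

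**There is discretion in reading the scans.** Section 11 has the neuroradiologist's reading set against the clinical course, and section 11.1 adds RANO criteria once published. A sensible reader might therefore call the progression anyway. Neither provision states a rule for non-target lesions, so this softens the point without closing it.

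**Growth of an irradiated lesion may be treatment effect.** This stands, and any added rule has to provide for it.

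**Stronger readings that the documents do not support.**

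- *Distant control counts these patients as successes.* The endpoint is undefined, so the text does not say so.
- *Resected lesions are missed in the same way.* A resected, unirradiated lesion can itself be targeted, and regrowth after complete resection can be read as a new lesion.
- *Between 6% and 12% of patients are missed failures.* That needs 20% to 40% with such a lesion and 30% of those growing (0.20 × 0.30 = 6%; 0.40 × 0.30 = 12%). Both inputs are assumptions. The product is also an upper figure under them, because patients with another PFS event first are not deducted.
- *One old-site necrosis closes the study by moving 3/36 to 4/36.* This depends on a denominator that section 5.9 does not give; 4/40 does not exceed 10%.
- *Section 5.9 should count only volumes irradiated on study.* The section speaks of the toxicity of the combination, which suggests that treatment-related necrosis was meant. TPI 287 is given systemically and studied as a radiosensitizer, so an effect at an old site cannot be ruled out from these documents. Narrowing a closure rule is contestable and does not follow from the gap.

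**Conclusion.** The progression gap holds. Applied as written, section 11.1 does not treat growth of a baseline non-target brain lesion as PD, so PFS is overstated for any patient in whom that growth precedes every other event. The direction is certain. The extent is not, because the number of such patients is unknown; one patient is 10 points in the 10-patient cohort. The finding rests on sections 3.1 and 3.2 governing over the stricter reading of the synopsis, and it is clearest for lesions with earlier focal radiation.

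For distant intra-cranial control the defect is a missing definition; no bias of known direction can be claimed. For necrosis, the finding is a mismatch between section 5.9 and section 5.4 on attribution and field, and the documents do not settle which was intended.

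The progression gap affects secondary endpoints in an uncontrolled, descriptively analysed phase 1 study. MTD determination is not directly affected.

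**What to change.** 1. **Section 11.1.** Add a rule: unequivocal progression of any non-target brain lesion present at baseline is PD and a PFS event. The neuroradiologist judges it against the clinical course and distinguishes it from treatment effect. It is reported as intracranial failure outside the target lesions, on its own line within or beside distant control.
2. **Section 14.1.** Define distant intra-cranial control so that it says where these lesions belong.
3. **Baseline form.** List every non-target brain lesion, with its earlier treatment, from the baseline MRI already required.
4. **Eligibility.** Reconcile the synopsis with sections 3.1 and 3.2 on earlier focal brain radiation.
5. **Section 5.9.** Reconcile the necrosis count with the attribution and irradiated-volume wording of section 5.4, and report necrosis by site. Which rule should apply is for the sponsor and the monitoring bodies to settle.

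The cost is a few sentences and one list, with no added visit, scan or patient. PFS and distant control will look slightly less favourable, and separating regrowth from treatment effect leaves some judgement to the reader of the scans.
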